5.0 Subject Disposition

A summary of subject accountability by investigators will be provided among the ITT Populations where the number of subjects in each of the following categories will be tabulated for each study for each treatment groups:

- Subjects in each analysis population (ITT, safety);
- Subjects who discontinued study treatment;
- Subjects who completed Period A;
- Subjects who completed the study.

A summary of subject disposition in Period A will be provided based on ITT Populations where the number and percentage of subjects in each of the following categories will be tabulated for each study for each treatment group:

- Subjects who were randomized in the study;
- Subjects who took at least one dose of study treatment in Period A;
- Subjects who completed study treatment in Period A;
- Subjects who discontinued study treatment in Period A (overall and by reasons);
- Subjects who discontinued study in Period A (overall and by reasons);
- Subjects who completed Period A.

Summaries of subject disposition in Period B will be provided based on ITT B Populations where the number of subjects in each of the following categories will be summarized for each study for each treatment group:

- Subjects who entered into Period B;
- Subjects who took at least one dose of study treatment in Period B;
- Subjects who completed protocol-specified treatment in Period B;
- Subjects who prematurely discontinued study treatment in Period B (overall and by reason);

- Subjects who prematurely discontinued study in Period B (overall and by reason);
- Subjects who completed the study in Period B.

6.0 Study Treatment Duration and Compliance

For the Safety Populations, duration of treatment will be summarized by descriptive statistics of mean, standard deviation, median, minimum and maximum for each study for each period for each treatment group, as well as ALL RZB Population for each study.

Duration of each treatment for each period is defined as following:

Study Treatment Duration in Period A for ITT Populations:

- For subjects who do not continue into Period B:
 - minimum of (the last dose date in Period A + 84, the end of study date (if not missing) + 1 day, [and the Primary Analysis cutoff date for Period A + 1 day]) minus the first dose date in Period A
- For subjects who continue into Period B:
 - minimum of (the last dose date in Period A + 84, first dose date in Period B, the end of study date (if not missing) + 1, [and the Primary Analysis cutoff date for Period A + 1 day]) minus the first dose date in Period A

Study Treatment Duration in Period B for ITT B Populations:

- For subjects who continue into Period B:
 - minimum of (the last dose date in Period B + 84 days, and the end of study date + 1, [and the Primary Analysis cutoff date for Period A + 1 day]) minus the first dose date in Period B

Study Treatment Duration under the Administration of RZB (Applicable for ALL RZB Populations Only):

- minimum of (the last date of RZB + 84 days, the end of study date + 1) minus the first dose date of RZB.

Treatment compliance will be summarized by treatment groups for each period for each study based on the Safety G and Safety S Populations, by visit and overall.

Compliance in Period A for Safety Populations:

- For Period A, the possible subcutaneous injections can happen at Baseline and Week 4.

The compliance for RZB and placebo will be summarized by the percentage of planned subcutaneous injections which are administered at each dosing visit and overall during Period A.

Compliance in Period B for Safety B Populations:

- For Period B, the possible subcutaneous injections can happen at Weeks 16, 28, and 40.

The compliance for subjects continued RZB and switched from placebo to RZB will be summarized by the percentage of planned subcutaneous injections which are administered at each dosing visit and overall during Period B.

When computing the compliance for each treatment group at a visit, the denominator will include all subjects who reached the visit. For subjects who prematurely discontinued before the dosing visit, the subject will not be counted for the planned injections.

7.0 Subject Characteristics

Categorical variables will be summarized with the number and percentage of subjects. Continuous variables will be summarized with descriptive statistics (number of

non-missing observations, mean and standard deviation, median, minimum and maximum).

7.1 Demographics and Baseline Characteristics

Demographics and baseline disease characteristics will be summarized descriptively, overall and by treatment group for the ITT Populations. Unless otherwise specified, baseline is defined as the last non-missing value prior to the first administration of study treatment (or randomization date if no study treatment was administered).

Continuous demographic variables include age, weight, height, and body mass index (BMI).

Categorical demographic variables include: sex, ethnicity (Hispanic or Latino, Not Hispanic or Latino), race, Age (< 40, ≥ 40 to < 65, ≥ 65 years), weight (≤ 100 kg, > 100 kg), BMI (normal: < 25; overweight: ≥ 25 to < 30; obese: ≥ 30 kg/m²), Nicotine user (current, former, never, unknown), alcohol user (current, former, never, unknown).

Baseline disease characteristics include BSA (< 10%, ≥ 10%), prior biologic therapies for psoriasis (0, ≥ 1), sPGA (3,4), sPGA-G (3,4) for Study-G only, scalp IGA (3,4) for Study-S only, PSSI (by median) for Study-S only.

Patient Reported Outcomes (PROs) analyzed at baseline include:

- Study-G: GPSS, GenPs-SFQ, PatGA-Genital, DLQI (Dermatology Life Quality Index), and HADS
- Study-S: PSS, Scalp Itch NRS (Numerical Rating Scale), DLQI, and HADS

In addition to the analysis of Itch NRS as a continuous variable, Itch NRS ≥ 4 will be summarized as a categorical baseline variable.

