3.9 Vital Signs

Vital sign determinations of systolic and diastolic blood pressure, pulse rate, respiratory rate, and body temperature will be obtained at visits as specified in Section 2.1. Blood pressure and pulse rate should be measured after the subject has been sitting for at least 3 minutes.

Measurements should be assessed consistently throughout the study. Vital signs measurements determined prior to dosing on Baseline/Day 1 or specify timing will serve as baseline.

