6 STUDY DRUG

6.1 Treatments Administered

The study drugs risankizumab or matching placebo will be administered by a healthcare professional in the form of an SC injection at the visits listed in Section 2.1.

Risankizumab and matching placebo will be provided by AbbVie as solution for injection in PFS.

During the 16-week double-blind placebo-controlled treatment period (Period A), subjects will receive 1 injection SC of risankizumab (150 mg total dosage, for those randomized to risankizumab) or matching placebo (for those randomized to placebo) at Baseline/Day 1 and Week 4. During the 36-week open-label treatment period (Period B), subjects will receive 1 injection SC of risankizumab (150 mg total dosage) at Weeks 16, 28 and 40. Study drug administration instructions will be provided separately.

Study drug must not be dispensed without contacting the IRT system. Study drug may only be dispensed to subjects enrolled in the study through the IRT system. At the end of the Treatment Period or at the Premature Discontinuation Visit, the site will contact the IRT system to provide visit date information.

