2.2 Study Design Overview

This is a Phase 4, multicenter, randomized, double-blind, placebo-controlled study examining the effect of RZB in adult subjects with moderate to severe genital psoriasis (Study-G) or moderate to severe scalp psoriasis (Study-S).

[figure not shown]
Participants will receive 150 mg of RZB (for those randomized to risankizumab) or matching placebo (for those randomized to placebo) subcutaneously at Baseline and Week 4. Starting at Week 16, all subjects will receive 150 mg of RZB every 12 weeks until the last dose at Week 40.

The duration of the studies will be approximately 64 weeks. Each study comprises a 30-day Screening Period, a 16-week double-blind placebo-controlled treatment period (Period A), a 36-week open-label treatment period (Period B), and an 8-week Follow-up Period. The follow-up phone call (20 weeks following the last dose of study drug) during the trial will not be required for any subject who initiates commercial RZB or continues

under another AbbVie protocol for the purposes of continued treatment (i.e., CTE or CTPP OLE).

The schematic of the study is shown in [Figure 1](#).

Figure 1. Study Schematic

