4.0 Analysis Populations

The following population will be used for the analyses.

The **Intent-to-Treat (ITT) Populations** include:

- ITT G, includes all subjects randomized in Study-G.
- ITT S, includes all subjects randomized in Study-S.

- ITT B G, includes all subjects randomized in Study-G and enter Period B.
- ITT B S, include all subjects randomized in Study-S and enter Period B.

The ITT G/ITT B G and ITT S/ITT B S Populations will be used for all efficacy analyses in Study-G and Study-S respectively. Subjects will be included in the analysis according to the treatment group to which they were randomized (as randomized).

The **Safety Populations** include:

- Safety G includes all subjects randomized to Study-G and received at least 1 dose of study drug.
- Safety S includes all subjects randomized to Study-S and received at least 1 dose of study drug.
- Safety B G includes all subjects randomized to Study-G and received at least 1 dose of study drug in Period B.
- Safety B S includes all subjects randomized to Study-S and received at least 1 dose of study drug in Period B.

For the Safety G/Safety B G and Safety S/Safety B S Populations, subjects will be analyzed according to treatment actually received (as treated), regardless of the treatment randomized. The treatment actually received is determined by the first dose of study drug that the subject received during the specific analysis period.

The **All Risankizumab Treated Populations** include:

- ALL RZB G: all subjects who receive at least 1 dose of RZB as the study drug in Study-G.
- ALL RZB S: all subjects who receive at least 1 dose of RZB as the study drug in Study-S.

All RZB treated populations will be utilized for a comprehensive safety summary of RZB.

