If there is a stratum with zero subjects in either treatment group, the 0 count will be replaced by 0.1 in order to prevent dividing by 0 in the above equations, as suggested in Greenland & Robins. In case of any stratum with zero subjects in both treatment groups, the corresponding stratification factor will not be controlled.

For continuous variables, the Baseline mean, visit mean, as well as the Least Square (LS) mean, 95% confidence interval (CI) and Standard Error (SE) of the mean, will be reported for each ITT Population. The comparisons between RZB and placebo will be analyzed using Mixed-Effect Model Repeated Measurement (MMRM) method, adjusting for the fixed effects of treatment, actual values of stratification factors at Baseline, Baseline value, visit and treatment by visit interaction as covariates.

"Baseline" refers to the last non-missing observation on or before the date of the first administration of study drug, or the date of randomization if no study drug is administered.

For analyses by stratification factors used for randomization, any subject who is randomized within an incorrect stratum will be analyzed according to the actual stratum to which the subject belongs.

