10.4 Analysis of Vital Signs

Vital sign measurements of systolic and diastolic blood pressure will be summarized.

Each vital sign variable will be summarized for all time points (starting with Baseline) with the number of non-missing observations, mean and standard deviation, median, minimum and maximum, in Period A (Safety Populations) and B (Safety B Populations). Mean change from baseline to each applicable post-baseline visit will be summarized for each vital sign variable, with the number of observations, baseline mean, and visit mean. The change from baseline mean, standard error, and 95% confidence interval will be presented for the mean change from baseline within each treatment group and difference between RZB vs. placebo.

Vital sign variables will be evaluated based on Potentially Clinically Significant (PCS) criteria ([Appendix C](#)). For each vital sign PCS criterion, the number and percentage of subjects who have a vital sign value meeting the criteria will be summarized in Period A (Safety Populations), B (Safety B Populations) and during the administration of risankizumab (ALL RZB Populations). Listings will be provided to summarize subject-level vital sign data for subjects meeting PCS.

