Appendix C. Potentially Clinically Significant Criteria for Safety Endpoints

The criteria for Potentially Clinically Significant (PCS) laboratory findings are described in Table C-1 and Table C-2, and the PCS criteria for vital sign findings are described in Table C-3.

Table C-1. Criteria for Potentially Clinically Significant Hematology Values

Hematology Variables	Units	Definition of Potentially Clinically Significant Current (Version 4.03) NCI CTCAE Grade 3 or Greater	
		Very Low	Very High
Hemoglobin	g/dL	< 8.0	
Platelets count	10 ⁹ /L	< 50.0	
WBC count	10 ⁹ /L	< 2.0	
Neutrophils	10 ⁹ /L	< 1.0	
Lymphocytes	10 ⁹ /L	< 0.5	

Note: A post baseline value must be more extreme than the baseline value to be considered a potentially clinically significant finding.

Table C-2. Criteria for Potentially Clinically Significant Chemistry Values

Chemistry Variables	Units	Definition of Potentially Clinically Significant Current (Version 4.03) NCI CTCAE Grade 3 or Greater	
		Very Low	Very High
TBL	mcmol/L		$> 3.0 \times \text{ULN}$
ALP	U/L		$> 5.0 \times \text{ULN}$
SGOT/AST	U/L		$> 5.0 \times \text{ULN}$
SGPT/ALT	U/L		$> 5.0 \times \text{ULN}$
Albumin	g/L	< 20	
Glucose	mmol/L	< 2.2	> 13.9
Triglycerides	mmol/L		> 5.7
Creatinine	mcmol/L		$> 3.0 \times \text{ULN} (> 3.0 \times \text{BL})$
Sodium	mmol/L	< 130	> 155
Potassium	mmol/L	< 3.0	> 6.0
Calcium	mmol/L	< 1.75	> 3.1
CPK	U/L		$> 5.0 \times \text{ULN}$
Total Cholesterol	mmol/L		> 10.34
GGT			$> 5.0 \times \text{ULN}$

Note: A post baseline value must be more extreme than the baseline value to be considered a potentially clinically significant finding.

Table C-3. Criteria for Potentially Clinically Significant Vital Sign Values

Vital Signs Variables	Criterion	Definition of Potentially Clinically Significant
Systolic Blood Pressure (mmHg)	Low	Value ≤ 90 mmHg and decrease ≥ 20 mmHg from Baseline
	High	Value ≥ 160 mmHg and increase ≥ 20 mmHg from Baseline
Diastolic Blood Pressure (mmHg)	Low	Value ≤ 50 mmHg and decrease ≥ 10 mmHg from Baseline
	High	Value ≥ 100 mmHg and increase ≥ 10 mmHg from Baseline

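### ALL RZB blood-pressure findings in former placebo subjects are measured from Day 1, before 16 weeks of placebo, instead of from the last value before risankizumab

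*SAP*

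**What the plan says.** **Baseline.** SAP 7.1 sets the default, unless something else is specified: "baseline is defined as the last non-missing value prior to the first administration of study treatment". SAP 9.1 has the same anchor for efficacy, where baseline "refers to the last non-missing observation on or before the date of the first administration of study drug". For vital signs, Operations Manual 3.9 (Protocol Appendix G) says: "Vital signs measurements determined prior to dosing on Baseline/Day 1 or specify timing will serve as baseline". Its option of another timing looks like an unfilled template field and names no other time point. Study drug includes placebo (Operations Manual 6.1): "The study drugs risankizumab or matching placebo will be administered by a healthcare professional". The first placebo injection therefore fixes a placebo subject's baseline.

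**Population.** SAP 4.0 defines the Study-G set as "all subjects who receive at least 1 dose of RZB as the study drug in Study-G", with a matching set for Study-S. SAP 2.2 adds: "Starting at Week 16, all subjects will receive 150 mg of RZB every 12 weeks until the last dose at Week 40". Placebo subjects who continue therefore join ALL RZB at Week 16.

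**Output.** SAP 10.4 tabulates blood-pressure PCS findings for Period A, for Period B and "during the administration of risankizumab (ALL RZB Populations"), with subject-level listings. The high systolic criterion in Table C-3 is "Value ≥ 160 mmHg and increase ≥ 20 mmHg from Baseline". The other three criteria (low systolic, low and high diastolic) also combine a level with a change from Baseline.

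**Other ALL RZB definitions.** Treatment-emergent adverse events (SAP 10.2.1), patient-years (SAP 10.2.4) and treatment duration (SAP 6.0) all start at the first risankizumab dose.

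**The concern.** A count labelled as occurring during risankizumab should compare on-drug values with the state just before the drug began. For former placebo subjects the stated rule compares them with a value taken 16 weeks before the first risankizumab dose. A change that arose on placebo and persisted is then booked to risankizumab. A fall on placebo can hide a later rise on risankizumab.

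Safety 10.1, 10.4 and Appendix C of the SAP give no separate baseline for ALL RZB, so a programmer following the text would carry the Day 1 value forward. At stake is whether the ALL RZB blood-pressure table and its listing name the right subjects.

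**Working it through.** The plan states no figure that depends on this definition, so there is none to reproduce. The check traces the rule, tests it on individual cases, and sizes the net effect under assumptions.

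**1. Who is affected.** SAP 2.4 plans 50 subjects per arm in each study. If all placebo subjects go on to risankizumab, 50 of about 100 ALL RZB subjects per study (half) are former placebo subjects. Dropout before Week 16 lowers this.

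**2. Whether a better reference value exists.** Vital signs are on the Week 16 visit list (Operations Manual 2.1), and dosing follows all other visit procedures except post-dose monitoring (Operations Manual 6.5). A Week 16 pre-dose reading is therefore already collected.

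**3. Individual cases.** High systolic PCS requires value ≥ 160 and value − baseline ≥ 20 mmHg.

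| Day 1 | Week 16 pre-dose | Week 28 | Change from Day 1 | Change from Week 16 | Day 1 rule | Week 16 rule |
|---|---|---|---|---|---|---|
| 138 | 162 | 161 | 161 − 138 = +23 | 161 − 162 = −1 | flagged | not flagged |
| 150 | 140 | 162 | 162 − 150 = +12 | 162 − 140 = +22 | not flagged | flagged |

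The first subject did not rise on risankizumab but is counted. The second rose 22 mmHg on risankizumab and is missed.

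**4. Net size.** The documents give no blood-pressure distribution, so these inputs are assumptions: systolic mean 130 to 135 mmHg, between-subject SD 13, slowly varying within-subject SD 7 (correlation 0.7 per 12 weeks), visit-to-visit SD 8, and no drug effect. In 400,000 simulated former placebo subjects, a flag is a value meeting the criterion at any of Weeks 28, 40 or 52. The lower figure in each pair belongs to mean 130, the higher to mean 135.

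| Shift by Week 16 that persists | Flagged, Day 1 baseline | Flagged, Week 16 baseline | Net excess per 50 |
|---|---|---|---|
| None | 2.7% to 4.3% | 2.4% to 3.8% | 50 × 0.003 = 0.15; 50 × 0.005 = 0.25 |
| +3 mmHg | 4.6% to 6.9% | 3.1% to 4.8% | 50 × 0.015 = 0.75; 50 × 0.021 = 1.05 |

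From unrounded rates and repeat runs, the net excess is about 0.1 to 0.2 subject with no shift and about 0.7 to 1.1 with the 3 mmHg rise.

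**5. Sensitivity to the model.** A second model (between-subject SD 12, independent visit SD 8 to 10, same means) gives practically equal rates under either baseline when there is no shift (1.0% to 4.3% each). If every subject rises 5 mmHg on placebo, it gives 3.3% to 9.7% (Day 1) against 1.8% to 6.4% (Week 16).

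**6. Laboratory tests.** Hematology and chemistry are scheduled at Screening, Baseline, Week 28 and Week 52 (Protocol Appendix D). None falls at Week 16, so the last scheduled value before risankizumab is Day 1 under either rule.

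**The case against.** **The carry-over is an inference.** SAP 10.4 defines no baseline. The general rule sits in a section on demographics and allows exceptions, SAP 9.1 concerns efficacy, and the Operations Manual sentence is incomplete. This is fair: the gap is better described as an unstated safety baseline than as a deliberate choice. But no other rule is written, so Day 1 is what the text yields.

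**The reach is narrow.** A reader might infer that the whole ALL RZB safety summary is mixed with placebo-period changes. The documents do not support that. Adverse events and exposure start at the first risankizumab dose, and SAP 10.4 plans mean blood-pressure change for Periods A and B only.

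**The direction is not fixed.** A reader might also infer that the rule always inflates risankizumab counts. The second case above shows the opposite. Nor does turnover of individual flags measure placebo effects. In the first model, 51% to 58% of Day 1 flags disappear under Week 16, but with no shift 45% to 48% of Week 16 flags are likewise absent under Day 1. Most of this is visit-to-visit variation around a single reading.

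**There is a partial safeguard.** The PCS listings could let a reader spot a case such as 138, 162, 161. They cannot reveal a missed case, because that subject is not listed.

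**A single baseline has merit.** In Period B it gives both original arms the same reference. That stands, and re-anchoring the Period B tables is a matter of preference.

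**Conclusion.** The point holds for the ALL RZB blood-pressure PCS counts and listing. As written, the plan measures former placebo subjects from before 16 weeks of placebo, which contradicts the label of the table and differs from every other ALL RZB time anchor. Individual misclassification in both directions follows from the rule itself and needs no model.

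The net bias is small unless pressure shifts during placebo: about 0.1 to 0.2 subject per 50 with no shift, and about 0.7 to 1.1 with a persistent 3 mmHg rise. These sizes rest on an assumed systolic distribution with no drug effect, and nothing in the documents indicates that such a shift will occur. Only changes that persist past Week 16 matter.

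Efficacy, adverse events, the randomised Period A comparison and scheduled laboratory summaries are unaffected. This is a modest correction to a descriptive output.

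**What to change.** Add to SAP 10.1 or 10.4: for vital-sign PCS analyses in the ALL RZB populations, baseline is the last non-missing value before the first risankizumab dose (the Week 16 pre-dose value for former placebo subjects), and only values after that dose count as post-baseline. The second clause keeps the Week 16 pre-dose reading, taken on the same date as the first risankizumab injection, from being counted as an on-drug value.

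The cost is one sentence and one extra derived baseline flag. No new data are needed. The downside is that the ALL RZB baseline will differ from the study baseline in the Period A and Period B tables, so the ALL RZB table and listing need a footnote saying so.

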7.2 Medical History and Prior and Concomitant Medications

Medical history data will be coded using the Medical Dictionary for Regulatory Activities (MedDRA). The actual version of the MedDRA coding dictionary will be noted in the statistical tables and clinical study report. The number and percentage of subjects in each medical history category (by MedDRA system organ class (SOC) and preferred term (PT)) will be summarized overall and by treatment group for each study for the ITT Populations. The SOC will be presented in alphabetical order, and the preferred terms will be presented in alphabetical order within each SOC. Subjects reporting more than one condition/diagnosis will be counted only once in each row (SOC or preferred term).

Prior and concomitant medications will be summarized separately. The number and percentage of subjects taking prior and concomitant medications will be summarized by generic drug name, based on the World Health Organization (WHO) Drug Dictionary. The actual version of the WHO Drug Dictionary will be noted in the statistical tables and clinical study report.

A prior medication is defined as any medication taken prior to the date of the first dose of study drug. A concomitant medication is defined as any medication that started prior to the date of the first dose of study drug and continued to be taken after the first dose of study drug or any medication that started on or after the date of the first dose of study drug, but not after the last dose of study drug plus 140 days.

A concomitant medication is defined as any medication that started prior to the date of the first dose of study drug and continued to be taken after the first dose of study drug in each period or any medication that started on or after the date of the first dose of study drug in each period, but not after:

For ITT Populations in Period A:

- For subjects who do not continue into Period B:
 - minimum of (the last dose date in Period A + 140, the end of study date (if not missing) + 1 day, [and the Primary Analysis cutoff date for Period A + 1 day])
- For subjects who continue into Period B:
 - minimum of (the last dose date in Period A + 140, first dose date in Period B, the end of study date (if not missing) + 1, [and the Primary Analysis cutoff date for Period A + 1 day])

For ITT B Populations in Period B:

- For subjects who continue into Period B:
 - minimum of (the last dose date in Period B + 140 days, and the end of study date + 1)

Prior medications will be summarized among the ITT Populations. Concomitant medications will be summarized for Period A among the ITT Populations, and for Period B among ITT B Populations.

